5.7.1.6. ARIA Data Handling Principles

If the radiographic severity of an ARIA event increases or the event changes from asymptomatic to symptomatic, additional AE records will be added to eCRF to capture the change with new start/end AE dates (the end date of the previous record will be the start date of the next record). For analysis, records with changes in severity or symptomatic status are considered as a single ARIA event. The severity/symptomatic status for that event is defined as the worst level among all the AE records that belong to that event.

In general, the start date of the event is the earliest start date among the AE records for the ARIA event, and the end date is the latest end date.

If the same type of ARIA event happens again after the previous event has ended, then it is considered a recurrent event. Recurrent events will be referred to as the second event, the third event, etc.

If the duration based on MRI for an ARIA-E event overlaps with the duration based on MRI for an ARIA-H event, then these two ARIA events will be defined as concurrent.

If a subject experienced ARIA-E but no ARIA-H then this ARIA-E event will be defined as isolated, and similarly for ARIA-H.

The MRI duration of an ARIA event is determined based on MRI assessments. The start date is the date of the MRI assessment that initially identifies the ARIA event, and the end date is the date of the MRI assessment that shows the complete resolution of this ARIA event (in the case of ARIA-E), or ARIA being stable (in the case of ARIA-H). Stable was defined as 'No change' or 'decrease' in number, size, severity, or number of locations of ARIA-H microhemorrhage or ARIA-H superficial siderosis between 2 consecutive MRIs.

The AE eCRF data will be used as the primary source for the ARIA analysis as it contains the complete information of ARIA as well as associated symptoms. The safety MRI data collected

under the 'Neurological Examination' eCRF page will only be used for specific analyses that require information that was not available in the AE eCRF.

5.7.1.7. Analysis of Adverse Events of Special Interest

ARIA (ARIA-E, ARIA-H) and cerebral hemorrhage > 1cm events will be summarized based on the Safety MRI Analysis Set. The incidence of ARIA events tables will summarize the number of subjects with any ARIA, ARIA-E, any ARIA-H, ARIA-H microhemorrhage, ARIA-H superficial siderosis, subjects experiencing both ARIA-E and ARIA-H, concurrent ARIA-E and ARIA-H, isolated ARIA-E and isolated ARIA-H.

Cerebral hemorrhage >1 cm will be summarized. Cerebral hemorrhages >1 cm will be identified by the eCRF and by using a customized MedDRA query, consisting of selected preferred terms within the Standardized MedDRA Query (SMQ) of "Haemorrhagic central nervous system vascular conditions (SMQ)" (narrow search). The customized query SMQ list may be modified based on newer version of MedDRA when available and safety team's discretion.

Seizures, hypersensitivity, and fall events will be summarized on the Safety Analysis Set. Seizures will be identified using a customized MedDRA query, consisting of selected preferred terms within the Standardized MedDRA Query (SMQ) of "Convulsions (SMQ)" (narrow search). ARIA status of subjects with seizures will be presented, splitting by the number of subjects with non-evaluable ARIA status (no post-baseline MRI), subjects with no ARIA event during the study and subjects who experienced ARIA during the study.

Hypersensitivity events will be identified using a customized MedDRA query, consisting of selected preferred terms within the Standardized MedDRA Query (SMQ) of "Hypersensitivity (SMQ)" (narrow scope). The hypersensitivity SMQ list may change due to newer version of MedDRA and at safety team's discretion.

Falls will be identified based on the preferred term "Fall" and number of falls will be presented by treatment group.

Other analyses of AEs within this SMQ may be performed, including exploration of potential association with ARIA-E. Analyses to describe and characterize the incidence of AESIs are listed in Table 5 below. Unless otherwise specified, results will be presented by treatment group.

Table 5 Analyses to Describe Incidence of AESIs and to Characterize AESI Events

Analysis		
Incidence of ARIA events		
Incidence of ARIA events by ApoE e4 genotype		
Maximum MRI severity and worst symptomatic status of ARIA events		
Maximum MRI severity and worst symptomatic status of ARIA events by ApoE genotype		
Maximum MRI severity and worst symptomatic status of ARIA events among participants with		
ARIA		
Onset of ARIA events		
Resolution of ARIA-E and stabilization of ARIA-H		
Recurrent ARIA-E		
ARIA-related adverse events by SOC/PT		

A	-	•
An	alv	ysis

Summary of symptomatic ARIA

Summary of serious and severe ARIA and symptoms

Serious or severe ARIA-related adverse events by PT

Cerebral hemorrhage > 1cm

Haemorrhagic CNS vascular conditions events by PT¹²

Haemorrhagic CNS vascular conditions events excluding subdural hematomas by PT¹²

Hypersensitivity events by PT¹³

Serious hypersensitivity events by PT¹³

Related hypersensitivity events by PT¹³

Seizures by PT¹³

Falls¹³

The following listings will also be provided with the relevant information:

- Listing of MRI assessments for subjects with ARIA-E
- Listing of MRI assessments for subjects with ARIA-H microhemorrhage
- Listing of MRI assessments for subjects with ARIA-H superficial siderosis
- Listing of MRI assessments for subjects with Cerebral hemorrhage > 1cm
- Listing of MRI assessments for subjects with other postbaseline MRI abnormalities
- Listing of MRI assessments for subjects with postbaseline MRI ischemic abnormalities
- Listing of ARIA-related adverse events for subjects with symptomatic ARIA based on Adverse Event CRF
- Listing of haemorrhagic CNS vascular conditions
- Listing of hypersensitivity adverse events
- Listing of seizures
- Listing of falls

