3.6. Analysis Sets

Randomized Set

The randomized set includes all the participants who were randomized.

Full Analysis Set (FAS)

The FAS includes all participants who were randomized and received at least 1 dose of study treatment (aducanumab or placebo). In analyses performed on the FAS, participants will be analyzed, based on the intention-to-treat principle, according to their randomized treatment assignment regardless of treatment received.

Safety Analysis Set

The Safety Analysis Set includes all participants who were randomized and received at least 1 dose of study treatment (aducanumab or placebo), essentially the same set of participants included in the FAS. In analyses performed on the Safety Analysis Set, participants will be analyzed according to their actual treatment received.

Safety MRI Analysis Set

The Safety MRI Analysis Set includes all participants who were randomized and received at least 1 dose of study treatment (aducanumab or placebo) and had at least one post-baseline MRI assessment.

Immunogenicity Analysis Set

The immunogenicity analysis set is defined as all participants in the safety analysis set who had at least 1 postdose sample evaluated for immunogenicity.

4. List of Planned Study Analyses

Below is a list of planned study analyses per protocol.

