5.7.2. Clinical Laboratory Evaluations

Clinical laboratory evaluations include hematology, blood chemistry and urinalysis. Baseline for laboratory parameters is defined as the last available value prior to the first dose.

For each laboratory category, the following analyses will be presented:

- Summaries of actual values by visit and respective figures displaying the mean values by visit
- Summaries of change from baseline by visit
- Summaries of percent change from baseline by visit

¹On safety population.

²Haemorrhagic CNS vascular conditions event is defined by haemorrhagic central nervous system vascular conditions SMQ (broad and narrow scope).

³Hypersensitivity reaction event is defined by hypersensitivity SMQ (narrow and broad scope), angioedema SMQ (narrow and broad scope) and anaphylactic reaction SMQ (narrow and broad scope).

⁴Seizures event is defined by Convulsions SMQ (broad and narrow scope).

⁵Fall event is defined by the preferred Term "Fall".

- Shift from baseline
- Potentially serious hepatotoxicity evaluation will be presented in a figure with respective listing. For subjects with potential serious hepatotoxicity, values over time will also be presented in a figure.

Note: Potentially serious hepatotoxicity is defined as ALT or AST > 3x ULN and total bilirubin > 2x ULN at any time post-baseline, not necessarily concurrent.

Potentially Clinically Significant laboratory abnormalities analyses

For hematology, blood chemistry and urinalysis, the number of subjects with potentially clinically significant laboratory abnormalities post-baseline will be summarized for the parameters provided in Table 6. Subjects need to have at least one post-baseline evaluation and a baseline value not potentially clinically significant (including missing) to be included in the analysis.

Table 6 Criteria to Determine Potentially Clinically Significant (PCS) Laboratory Abnormalities

Clinical Laboratory Abnormality Criteria					
Parameter name	PCS Low	PCS High			
HEMATOLOGY					
White blood cells	<3.0 x 109/L	>16 x 109/L			
Lymphocytes	<0.8 x 109/L	>12 x 109/L			
Neutrophils	<1.5 x 109/L	>13.5 x 109/L			
Monocytes	N/A	>2.5 x 109/L			
Eosinophils	N/A	>1.6 x 109/L			
Basophils	N/A	>1.6 x 109/L			
Red blood cells	≤3.5 x 1012/L	≥6.4 x 1012/L			
Hemoglobin - Females	≤95 g/L	≥175 g/L			
Hemoglobin - Males	≤115 g/L	≥190 g/L			
Hematocrit - Females	≤32%	≥54%			
Hematocrit - Males	≤37%	≥60%			
Platelet count	≤75 x 109/L	≥700 x 109/L			
BLOOD CHEMISTRY					

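### The cerebral hemorrhage > 1 cm table requires a post-baseline MRI although the event can be recorded without one, so a bleed in a participant never scanned after baseline is left out of it

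*SAP*

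**What the plan says.** SAP 5.7.1.7 assigns the analysis set: "ARIA (ARIA-E, ARIA-H) and cerebral hemorrhage > 1cm events will be summarized based on the Safety MRI Analysis Set". SAP 3.6 defines that set as randomized participants who received "at least 1 dose of study treatment (aducanumab or placebo) and had at least one post-baseline MRI assessment".

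The same SAP section says how the bleed is found: "Cerebral hemorrhages >1 cm will be identified by the eCRF and by using a customized MedDRA query". The query consists of selected preferred terms from the narrow search of the hemorrhagic CNS SMQ. SAP Table 4 adds that the eCRF has a fixed verbatim term for this event and that it can be coded to various preferred terms.

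SAP Table 5 lists the cerebral hemorrhage > 1 cm summary without a footnote. The next row reads "Haemorrhagic CNS vascular conditions events by PT¹²", and footnote 1 to that table is "¹On safety population". The hypersensitivity, seizure and fall rows carry the same footnote 1.

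For seizures, SAP 5.7.1.7 uses the Safety Analysis Set and gives participants without a post-baseline MRI their own category when ARIA status is shown.

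**The concern.** For ARIA-E and ARIA-H an MRI-based denominator is natural, because an unscanned participant cannot be shown to have the finding. Cerebral hemorrhage > 1 cm differs under the SAP's own rule: an eCRF entry or a qualifying coded term is enough, and either could rest on CT or a clinical diagnosis. The numerator can be met without an MRI, while membership of the set cannot.

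The resulting exclusion can depend on the outcome. A participant who dies of a bleed before any post-baseline scan is removed because of the event that the table is meant to count. SAP 5.1.1 plans no statistical testing, so descriptive counts are the whole safety result, and this is the only summary dedicated to bleeds of this size.

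**Working it through.** The plan states no figure for this point that could be reproduced. The check traces who enters the table, then illustrates the size under stated assumptions.

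**Who is counted**

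Inputs:
- The first scheduled post-baseline MRI is at Week 14, Day 99 (Protocol 1.3, Table 1). Doses fall on Days 1, 29, 57 and 85 before it, so there are four.
- After a hemorrhage > 1 cm, the protocol asks for an unscheduled MRI every 4 weeks until stable (Protocol 5.3.1.4).
- A brain MRI is planned at the early termination (ET) and follow-up visits (Protocol 1.3, Table 2), and this was kept after the study was stopped (SAP Table 1).
- The ET visit is not expected after death or withdrawal of consent (Protocol 8.3). Participants who start a disease-modifying treatment outside the trial complete no further visits (SAP Table 1, footnote 2).
- SAP 3.6 accepts any post-baseline MRI, scheduled or not.

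| Participant with a bleed > 1 cm | In the Safety MRI set? | In the > 1 cm table? |
|---|---|---|
| Scanned before the bleed, fatal or not | Yes | Yes |
| Not scanned before, scanned afterwards | Yes | Yes |
| Never scanned after baseline | No | No |

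Only the last row is lost.

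Early termination leaves some participants dependent on the ET or follow-up scan. Dosing could continue to 1 May 2024 (SAP 2.2.3). Day 99 is 98 days after the first dose, and 98 days before 1 May 2024 is 24 January 2024. Anyone first dosed after 24 January therefore could not reach the nominal Week 14 scan day by 1 May.

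**Direction**

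Let N be the Safety Analysis Set in one arm, u the share never scanned, k all bleeds and x the bleeds among those never scanned. The planned table shows (k − x) / [N(1 − u)] and the Safety Analysis Set gives k / N. The planned figure is lower exactly when x / k > u. If x = 0 it is slightly higher, because only the denominator shrinks.

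**Illustration (assumed values)**

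SAP 2.2.3 reports over 1000 enrolled. Taking exactly 1000, all dosed, at 2:1 gives N = 1000 × 2/3 ≈ 667 on aducanumab. With u assumed at 2% to 10%, the MRI set is 667 × 0.98 ≈ 654 down to 667 × 0.90 ≈ 600.

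| Bleeds k | Never scanned x | Planned table | Safety Analysis Set |
|---|---|---|---|
| 3 | 1 | 2/654 to 2/600 = 0.31% to 0.33% | 3/667 = 0.45% |
| 2 | 1 | 1/654 to 1/600 = 0.15% to 0.17% | 2/667 = 0.30% |
| 3 | 0 | 3/654 to 3/600 = 0.46% to 0.50% | 3/667 = 0.45% |

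**What the other outputs recover**

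The hemorrhagic CNS tables run on the safety population and use the broad and narrow SMQ, so they contain the narrow terms of the > 1 cm query. They are by preferred term with no size criterion. Because Table 4 allows a > 1 cm bleed to be coded to various terms, the > 1 cm count by arm cannot be read from them.

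**The case against.** The strongest defence is that the protocol describes this event by its diameter on a T2* MRI sequence (Protocol 5.3.1.4 and 8.1). For an event described on MRI, a denominator of participants with an MRI is a reasonable choice. That explains the choice, but the SAP's identification rule is wider than the protocol's description, and the mismatch remains.

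A reader might infer that early or fatal bleeds in general drop out. The documents do not support this. A fatal bleed in someone already scanned is counted, and so is an early bleed followed by the protocol's repeat MRIs or an ET scan. Week 14 is only the first scheduled scan, not the condition for entry.

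A reader might also infer that such a bleed disappears from the report. It does not. The safety-population hemorrhage tables and listing, SAEs by term (SAP 5.7.1.3), fatal events and the death listing (SAP 5.7.1.2) carry no MRI condition. The listing of all AEs shows the investigator term (SAP 5.7.1.1), so a bleed entered under the fixed eCRF term can be found by participant. This largely answers any worry about concealment. It does not supply the > 1 cm summary by arm.

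Finally, the report is abbreviated and descriptive, and no inference rests on this denominator. That stands, and it limits the severity.

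**Conclusion.** The point holds in a narrow form. The dedicated > 1 cm table omits a bleed in a participant with no post-baseline MRI at any time, although the SAP's identification rule would accept that bleed.

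The size is unknown, because the documents give neither event counts nor the number never scanned. It is probably small, given the scans required after a bleed and at the ET and follow-up visits. The reductions illustrated above presuppose that one of two or three bleeds was unscanned and say nothing about how likely that is. A reader might take the table to be biased downwards as a rule. That does not follow: the incidence is understated only if a never-scanned participant bled, and otherwise it is slightly overstated.

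Minor severity. It is worth correcting because the omission can be caused by the outcome itself, and the by-term tables do not replace the missing count.

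**What to change.** Run the cerebral hemorrhage > 1 cm row of SAP Table 5 on the Safety Analysis Set by adding footnote 1, and amend the sentence in SAP 5.7.1.7 to match. By arm, show how many participants had no post-baseline MRI and how many of those had the event, following the approach already used for seizures. Keep the Safety MRI set figure as supplementary, since the protocol describes the event on a T2* sequence. Leave ARIA-E and ARIA-H on the Safety MRI set.

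The cost is one more denominator in one descriptive table, with no new data. The downside is that unscanned participants count as event-free unless a bleed is recorded, which is why the number unscanned should be shown beside the result.

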5.7.2. Clinical Laboratory Evaluations

Clinical laboratory evaluations include hematology, blood chemistry and urinalysis. Baseline for laboratory parameters is defined as the last available value prior to the first dose.

For each laboratory category, the following analyses will be presented:

- Summaries of actual values by visit and respective figures displaying the mean values by visit
- Summaries of change from baseline by visit
- Summaries of percent change from baseline by visit

¹On safety population.

²Haemorrhagic CNS vascular conditions event is defined by haemorrhagic central nervous system vascular conditions SMQ (broad and narrow scope).

³Hypersensitivity reaction event is defined by hypersensitivity SMQ (narrow and broad scope), angioedema SMQ (narrow and broad scope) and anaphylactic reaction SMQ (narrow and broad scope).

⁴Seizures event is defined by Convulsions SMQ (broad and narrow scope).

⁵Fall event is defined by the preferred Term "Fall".

- Shift from baseline
- Potentially serious hepatotoxicity evaluation will be presented in a figure with respective listing. For subjects with potential serious hepatotoxicity, values over time will also be presented in a figure.

Note: Potentially serious hepatotoxicity is defined as ALT or AST > 3x ULN and total bilirubin > 2x ULN at any time post-baseline, not necessarily concurrent.

Potentially Clinically Significant laboratory abnormalities analyses

For hematology, blood chemistry and urinalysis, the number of subjects with potentially clinically significant laboratory abnormalities post-baseline will be summarized for the parameters provided in Table 6. Subjects need to have at least one post-baseline evaluation and a baseline value not potentially clinically significant (including missing) to be included in the analysis.

Table 6 Criteria to Determine Potentially Clinically Significant (PCS) Laboratory Abnormalities

Clinical Laboratory Abnormality Criteria					
Parameter name	PCS Low	PCS High			
HEMATOLOGY					
White blood cells	<3.0 x 109/L	>16 x 109/L			
Lymphocytes	<0.8 x 109/L	>12 x 109/L			
Neutrophils	<1.5 x 109/L	>13.5 x 109/L			
Monocytes	N/A	>2.5 x 109/L			
Eosinophils	N/A	>1.6 x 109/L			
Basophils	N/A	>1.6 x 109/L			
Red blood cells	≤3.5 x 1012/L	≥6.4 x 1012/L			
Hemoglobin - Females	≤95 g/L	≥175 g/L			
Hemoglobin - Males	≤115 g/L	≥190 g/L			
Hematocrit - Females	≤32%	≥54%			
Hematocrit - Males	≤37%	≥60%			
Platelet count	≤75 x 109/L	≥700 x 109/L			
BLOOD CHEMISTRY					
Alanine aminotransferase (ALT)	N/A	>3 x ULN			
Aspartate aminotransferase (AST)	N/A	>3 x ULN			
Alkaline phosphatase (ALP)	N/A	>3 x ULN			
Total bilirubin	N/A	>1.5 x ULN			
Blood urea nitrogen (BUN)	N/A	≥10.7 mmol/L			
Creatinine	N/A	≥176.8 umol/L			
Sodium	≤126 mmol/L	≥156 mmol/L			
Potassium	≤3 mmol/L	≥6 mmol/L			
Chloride	≤90 mmol/L	≥118 mmol/L			
Bicarbonate	≤16 mmol/L	≥35 mmol/L			

Glucose	≤2.2 mmol/L	≥9.7 mmol/L		
Calcium	≤2 mmol/L	≥3 mmol/L		
Phosphorus	≤0.6 mmol/L	≥1.7 mmol/L		
Albumin	≤25 g/L	≥625 g/L		
Total protein	≤45 g/L	≥100 g/L		
URINALYSIS				
Glucose	N/A	≥++++		
Ketones	N/A	≥++++		
Protein	N/A	≥++		
ULN = upper limit of normal				

5.7.3. Vital Signs

Vital sign parameters include body temperature, systolic blood pressure, diastolic blood pressure, heart rate, respiration rate, and body weight. Baseline is defined in a similar way as with clinical laboratory parameters.

Clinically relevant post-baseline abnormalities in vital signs will be presented with criteria defined below:

- $< 36 \, ^{\circ}\text{C}$ and $> 38 \, ^{\circ}\text{C}$ for body temperature
- < 60 bpm and > 100 bpm for pulse
- < 90 mmHg, > 140 mmHg and > 160 mmHg for systolic blood pressure
- < 50 mmHg, > 90 mmHg and > 100 mmHg for diastolic blood pressure
- \geq 7% increase and \geq 7% decrease from baseline in weight
- < 12 breaths/min and > 20 breaths/min for respiratory rate

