- 9. History of unstable angina, myocardial infarction, chronic heart failure (New York Heart Association Class III or IV), or clinically significant conduction abnormalities (e.g., unstable atrial fibrillation) within 1 year prior to Screening.
- 10. Clinically significant 12-lead ECG abnormalities as determined by the Investigator.
- 11. Uncontrolled hypertension defined as: average of 3 SBP/DBP readings > 165 mmHg and/or > 100 mmHg at Screening (blood pressure measurements exceeding these limits may be repeated as warranted by the Investigator, but values must be within the specified limits for the participant to be eligible for the study); or persistent SBP/DBP readings > 180 mmHg and/or > 100 mmHg 3 months prior to randomization (Day 1) that, in the opinion of the Investigator, are indicative of chronic uncontrolled hypertension.
- 12. History of malignancy or carcinoma. The following exceptions may be made after discussion with the Sponsor:
  - Participants with cancers in remission  $\geq 5$  years prior to Screening Visit 1.
  - Participants with a history of excised or treated basal cell or squamous carcinoma of the skin.

- Participants with localized prostate cancer with treatment cycles that completed at least 6 months prior to Screening Visit 1.
- 13. History of seizures or new-onset seizures within 10 years prior to Screening.
- 14. Indication of impaired liver function as shown by an abnormal liver function profile at Screening (e.g., repeated values of AST and ALT  $\geq 2 \times$  the upper limit of normal).
- 15. History or evidence of an autoimmune disorder considered clinically significant by the Investigator.
- 16. Recent history (within 1 year of Screening) of alcohol or substance abuse as determined by the Investigator, or a positive urine drug test (due to a nonprescription drug and without a clear justification of the results according to the Investigator) at Screening.
- 17. Within 30 days of Screening, clinically significant systemic illness or infection that requires hospitalization or that, in the opinion of the Investigator, is impacting the patient's usual performance in function or cognition.
- 18. History of or known seropositivity for HIV.

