5.7.5. Electrocardiograms

The 12-lead electrocardiograms (ECG) data will be summarized using shift table based on subjects with at least one post-baseline ECG assessment and whose baseline ECG assessment was not abnormal. This includes shift from normal or unknown at baseline to abnormal post-baseline, shift from normal or unknown at baseline to not adverse event or abnormal post-baseline, and shift from normal or unknown at baseline to adverse event post-baseline.

The number and percentage of subjects with shifts to abnormal ECG, not adverse events, and subjects with shift to abnormal ECG, adverse events at any time during post-baseline will be summarized. The ECG outlier in the uncorrected QT and Fridericia's corrected QTc intervals are the values exceeding a threshold of particular concern in clinical trials and are defined using criteria listed in FDA guidance - E14 Clinical Evaluation of QT/QTc Interval Prolongation and Proarrhythmic Potential for Non-Antiarrhythmic Drugs. The number and percentage of subjects

with ECG outlier in the uncorrected QT and Fridericia's corrected QTc interval will be summarized by treatment group.

- Absolute QTc interval prolongation:
 - \circ OTc interval > 450
 - o QTc interval > 480
 - o QTc interval > 500
- Change from baseline in QTc interval:
 - O QTc interval increases from baseline > 30
 - O QTc interval increases from baseline > 60

Baseline is defined in a similar way as with clinical laboratory data. The worst post-baseline value of each subject will be used.

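### SAP 5.7.3 presents post-baseline vital-sign abnormalities against absolute cut-offs with no condition on baseline, so a count over all post-baseline readings mixes pre-existing with new blood-pressure abnormalities

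*SAP*

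**What the plan says.** SAP 5.7.3 (Vital Signs) announces the table: "Clinically relevant post-baseline abnormalities in vital signs will be presented with criteria defined below". The blood-pressure criteria are absolute: "< 90 mmHg, > 140 mmHg and > 160 mmHg for systolic blood pressure" and "< 50 mmHg, > 90 mmHg and > 100 mmHg for diastolic blood pressure". Temperature, pulse and respiratory rate also have absolute limits. Only weight is judged against the participant's own starting value (a change of 7% or more, including "decrease from baseline in weight"). The section defines a baseline ("Baseline is defined in a similar way as with clinical laboratory parameters"), but no criterion except weight uses it. It does not say whether counting is at any time or by visit.

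Two neighbouring sections do condition on baseline:

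- SAP 5.7.2, potentially clinically significant laboratory values: a participant needs a post-baseline evaluation and "a baseline value not potentially clinically significant (including missing) to be included in the analysis".
- SAP 5.7.5, ECG shift table: limited to participants with a post-baseline ECG and "whose baseline ECG assessment was not abnormal".

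On entry, Protocol 6.2, exclusion criterion 11, removes participants with an "average of 3 SBP/DBP readings > 165 mmHg and/or > 100 mmHg at Screening", and those with persistently higher readings in the preceding 3 months that the investigator regards as chronic uncontrolled hypertension. Protocol 12.5.5 says only that the analysis will concentrate on clinically relevant abnormalities.

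**The concern.** Three of the blood-pressure criteria lie inside the range that eligibility allows. A participant can therefore meet a criterion before the first infusion, meet it again afterwards, and be counted as having a post-baseline abnormality although nothing has changed.

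After early termination, the report is mainly a safety summary. The abnormality count is the only vital-sign analysis that 5.7.3 describes, whereas laboratory data also get change-from-baseline summaries and shifts. As specified, a reader of the vital-sign table cannot tell pre-existing from new findings, the rates in both arms look high, and any real difference between arms is harder to see.

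**Working it through.** The plan gives no figure for this table, so there is nothing to reproduce. The check has two parts.

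**1. Cut-offs against the entry limits (whole mmHg)**

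| Criterion (SAP 5.7.3) | Highest admitted screening average (Protocol 6.2) | Already met by an admitted participant? |
|---|---|---|
| SBP > 140 | 165 | Yes, 141 to 165 |
| SBP > 160 | 165 | Yes, 161 to 165 |
| DBP > 90 | 100 | Yes, 91 to 100 |
| DBP > 100 | 100 | No |

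For pulse, temperature and respiratory rate, the baseline condition is also absent, but the protocol sets no numeric entry limit to compare. Weight is unaffected. The treatment-emergent rule in SAP 3.3 and 5.7.1 covers adverse events only. The windows in SAP 9.1.3 assign readings to visits and do not impose a baseline condition.

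**2. Effect on an any-time count**

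For one criterion, let b be the share meeting it at baseline (equal in both arms in expectation under randomisation), q the chance that such a participant is flagged again, and p the rate in participants who did not meet it at baseline.

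- Rate shown in an arm = b·q + (1 - b)·p
- Difference shown = b·(q1 - q0) + (1 - b)·(p1 - p0), where 1 is aducanumab and 0 is placebo
- If q1 = q0, the difference shown = (1 - b)·(p1 - p0)

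The documents give none of b, q or p. As an illustration only, assume p0 = 20%, p1 = 30% and q = 0.9 in both arms. The restricted table would then show 20% vs 30%: 10 points, ratio 1.50. The unrestricted table would show:

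| b | Placebo | Aducanumab | Difference | Ratio | Pre-existing share of flagged placebo participants |
|---|---|---|---|---|---|
| 10% | 0.09 + 0.18 = 27% | 0.09 + 0.27 = 36% | 9 points | 1.33 | 0.09/0.27 = 33% |
| 20% | 0.18 + 0.16 = 34% | 0.18 + 0.24 = 42% | 8 points | 1.24 | 0.18/0.34 = 53% |
| 30% | 0.27 + 0.14 = 41% | 0.27 + 0.21 = 48% | 7 points | 1.17 | 0.27/0.41 = 66% |
| 40% | 0.36 + 0.12 = 48% | 0.36 + 0.18 = 54% | 6 points | 1.125 | 0.36/0.48 = 75% |

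With q = 1.0 the differences are the same and the ratios are 1.32, 1.22, 1.16 and 1.12.

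A smaller assumed effect behaves the same way. With p0 = 30%, p1 = 36%, q = 0.95 and b = 30%, the rates are 0.285 + 0.210 = 49.5% and 0.285 + 0.252 = 53.7%. That is 4.2 points instead of 6, and a ratio of 1.08 instead of 1.20.

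**The case against.** Several counter-arguments have force.

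- **No uniform rule is broken.** A reader might infer that vital signs are the one domain where the SAP drops its own convention. The documents do not support that. In 5.7.5 the absolute QTc outlier counts use the worst post-baseline value with no stated baseline filter, and in 5.7.2 the potentially serious hepatotoxicity display has none either. The contrast holds for the laboratory table and the ECG shift table only. The QTc cut-offs are at least accompanied by change-from-baseline criteria, which blood pressure lacks.
- **Silence is not a decision.** SAP 5.7.3 does not say that baseline-abnormal participants are to be counted, and it does not call the findings new. Table 8 in 9.1.3 has a baseline row and visit windows, so a display by visit is possible. That would reduce repeated-reading flags and could show the starting rate. But 5.7.3 specifies no such display, and nothing in it excludes pre-existing cases.
- **Near-automatic re-flagging is not shown.** A reader might infer it from the 27 analysis visits in Table 8 from Week 4 to Week 104. The first participant was dosed on 27 July 2022 and dosing ended by 1 May 2024: 644 days, or 644/7 = 92 weeks at most. A participant first dosed on 31 January 2024 had 91 days, enough for three further infusions at 28-day intervals (91/28 = 3.25).
- **The excess count of participants is unchanged.** With b = 30% in the main illustration, the excess is 7 per 100 dosed, or 7 among the 70 at risk (10%). Only the denominator moves the difference. That is correct, but the ratio is still pulled towards 1 and the reader still cannot separate old from new.
- **There is partial cover elsewhere.** Under Protocol 11.1.1, an abnormal reading that is clinically significant or needs corrective treatment is an adverse event, and SAP 5.7.1 analyses adverse events by onset or worsening after first dose. This catches what investigators report, not every threshold crossing.

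**Conclusion.** The point holds as a minor improvement to a descriptive table. As written, 5.7.3 allows participants who entered with SBP above 140, SBP of 161 to 165, or DBP above 90 mmHg to be counted alongside new abnormalities, and it describes no shift or change-from-baseline display to separate them.

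The consequence is inflated rates in both arms and, with equal re-flagging, an absolute difference multiplied by (1 - b). The equal-re-flagging result assumes an any-time count and no treatment effect on readings in participants abnormal at baseline. The size in this trial is unknown; the percentages in the working illustrate the mechanism and are not estimates.

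Two stronger conclusions are tempting. One is that the table favours an arm. Randomisation balances baseline abnormality in expectation, and SAP 5.1.1 rules out statistical testing, so the effect is dilution rather than directional bias. The other is that the eligibility argument reaches every criterion, including pulse below 60. It does not: exclusion criterion 11 limits blood pressure only, and DBP above 100 lies outside the admitted screening average.

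**What to change.** Add to SAP 5.7.3: for each absolute vital-sign criterion, the table counts participants with at least one post-baseline value and a baseline value that does not meet that criterion, with missing baselines included. State that number as the denominator, and say whether counting is at any time or by visit. Leave weight as it is, since it is already relative to baseline.

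Add a shift table of baseline category by worst post-baseline category for systolic and diastolic pressure, so that worsening in participants abnormal at baseline remains visible.

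The cost is a sentence or two, a filter on data already collected, a smaller denominator for each criterion, and one extra table. If the database is already locked, SAP 5.1.1 allows further ad hoc analyses, with significant changes recorded in the clinical study report.
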